2.3.1 Potential Risks and Benefits

Inosine's reputation as an athletic performance enhancer has led to its widespread marketing and use as a nutritional supplement. Potential side effects of inosine relate to the resulting elevated urate (uric acid) levels (hyperuricemia). Hyperuricemia has been linked to gout. Gout generally develops in people with serum urate concentrations above 8 mg/dL (the upper limit of the normal range). Hyperuricemia has also been linked to the formation of urate stones in the kidneys or ureters (urolithiasis). Urate urolithiasis account for 5 to 10 percent of urinary tract stones in the United States and Europe. In most urate stone formers the primary pathophysiologic defect, however, is an excessively acidic urine pH rather than hyperuricemia and hyperuricosuria⁵². High urate levels have also been associated with high blood pressure and increased risk for cardiovascular events. However, whether a causal relationship between high urate and cardiovascular disease exists is unclear⁵³.

Considerable non-clinical human experience on inosine has been gained from the widespread use of inosine as a nutritional supplement and a purported (but unsubstantiated) athletic performance

enhancer. Although inosine use has been generally considered safe in these contexts, exposures are variable in size and poorly documented.

Three exercise physiology studies of oral inosine on athletic performance in humans have been published⁵⁴⁻⁵⁶. All three reported that multi-gram doses (up to 10 gm/day) were well tolerated short-term (up to 10 days), but had no demonstrable benefit on athletic performance.

Of relevance to the proposed study, multi-year clinical trials of oral inosine in multiple sclerosis (MS) and Parkinson's disease (PD) at doses comparable to those planned here have been conducted. In these studies, inosine at doses sufficient to chronically elevate urate into the ranges targeted here was well tolerated, with the most consistent AE being the rare development of uric acid urolithiasis.

The MS literature includes 4 peer-reviewed published studies on the use of inosine^{51, 57-59}. Inosine has been administered in this population for prolonged periods (up to 1 year) at up to 3 gm/day (divided into 2 or 3 doses daily).

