In the recent SURE-PD trial²¹, a total of 75 subjects with Parkinson's Disease (mean age, 62 years; 55% women) were randomized to either placebo or inosine titrated to produce mild (6.1-7 mg/dL) or moderate (7.1-8 mg/dL) serum urate elevation and were followed for up to 24 months. Individuals at greatest risk of known effects of increased urate (i.e., those with a history of gout or urolithiasis, or with urine pH \leq 5.0, a major risk factor for uric acid urolithiasis) were excluded from enrolling. Treatment was initiated gradually with 1 capsule (500 mg of inosine per capsule) taken 2 times daily for 2 weeks. After the 2- and 4-week visits, participants received up to 2 capsules 2 to 3 times daily, as algorithmically determined by serum urate concentration and treatment group assignment. Target urate levels were achieved between 2 and 4 weeks after initiation of inosine treatment²¹. Serious adverse events (17), including infrequent cardiovascular events, occurred at the same or lower rates in the inosine groups relative to placebo. No participant developed gout and 3 receiving inosine developed symptomatic nephrolithiasis (6%); two were determined to be calcium oxalate stones and one was believed to be a uric acid stone. Despite the increased frequency of nephrolithiasis while receiving inosine, there were no other renal SAEs and renal function measures of glomerular filtration rate and serum creatinine remained unchanged from baseline in all groups. Serial vital signs, serum assays, and electrocardiograms showed no effect of inosine on blood pressure, body mass index, serum glucose and cholesterol levels or electrocardiographic parameters. Treatment was tolerated by 95% of participants at 6 months, and no participant withdrew because of an adverse event. Serum urate rose by 2.3 and 3.0 mg/dL in the 2 inosine groups ($P < .001$ for each) vs. placebo, and cerebrospinal fluid urate level was greater in both inosine groups ($P = .006$ and $< .001$, respectively). Secondary analyses demonstrated non-futility of inosine treatment for slowing disability.

The Phase III SURE-PD3 trial is ongoing and the goal is to enroll 270 subjects with Parkinson's Disease by December 2017.

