9.1 Definitions of AEs, Suspected Adverse Drug Reactions & SAEs

9.1.1 Adverse Event and Suspected Adverse Drug Reactions

An adverse event (AE) is any unfavorable and unintended sign (including a clinically significant abnormal laboratory finding, for example), symptom, or disease temporally associated with a study, use of a drug product or device whether or not considered related to the drug product or device.

Adverse drug reactions (ADR) are all noxious and unintended responses to a medicinal product related to any dose. The phrase “responses to a medicinal product” means that a causal relationship between a medicinal product and an adverse event is at least a reasonable possibility, i.e., the relationship cannot be ruled out. Therefore, a subset of AEs can be classified as suspected ADRs, if there is a causal relationship to the medicinal product.

Examples of adverse events include: new conditions, worsening of pre-existing conditions, clinically significant abnormal physical examination signs (i.e. skin rash, peripheral edema, etc), or clinically significant abnormal test results (i.e. lab values or vital signs), with the exception of outcome measure results, which are not being recorded as adverse events in this trial (they are being collected, but analyzed separately). Stable chronic conditions (i.e., diabetes, arthritis) that are present prior to the start of the study and do not worsen during the trial are NOT considered adverse events. Chronic conditions that occur more frequently (for intermittent conditions) or with greater severity, would be considered as worsened and therefore would be recorded as adverse events.

Adverse events are generally detected in two ways:

Clinical → symptoms reported by the subject or signs detected on examination.

Ancillary Tests → abnormalities of vital signs, laboratory tests, and other diagnostic procedures (other than the outcome measures, the results of which are not being captured as AEs).

For the purposes of this study, symptoms of progression/worsening of ALS, including ‘normal’ progression, will be recorded as adverse events.

The following measures of disease progression will not be recorded as adverse events even if they worsen (they are being recorded and analyzed separately): vital capacity results and ALSFRS-R results.

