If discernible at the time of completing the AE log, a specific disease or syndrome rather than individual associated signs and symptoms should be identified by the Site Investigator and recorded on the AE log. However, if an observed or reported sign, symptom, or clinically significant laboratory anomaly is not considered by the Site Investigator to be a component of a specific disease or syndrome, then it should be recorded as a separate AE on the AE log. Clinically significant laboratory abnormalities, such as those that require intervention, are those that are identified as such by the Site Investigator.

Subjects will be monitored for adverse events from the time they sign consent until completion of their participation in the study (defined as death, consent withdrawal, loss to follow up, early study termination for other reasons or following completion of the entire study).

The following will be considered Adverse Events of Special Interest regardless of severity: nephrolithiasis, urolithiasis, and gouty arthritis.

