10.2.2 Outcomes

10.2.2.1 Safety outcomes

The proportion of subjects experiencing one or more adverse events (AE) prior to treatment, one or more treatment-emergent (TE, defined as occurring any time after first dose of study drug) AEs, one or more severe TE AEs, one or more serious TE AEs (SAE), one or more TE AEs of special interest (AESI, including gout, gouty arthritis, and kidney stones), and one or more AEs classified by MedDRA system organ class, higher level term, and preferred term over 24 weeks in the inosine group will be compared to the placebo group using one-tailed Fisher's exact tests at $\alpha = 0.05$. The proportion of subjects experiencing one or more TE clinically significant abnormal labs for each safety assay performed or clinically significant abnormal vital signs for each vital sign monitored over 24 weeks in the inosine group will be compared to the placebo group using Fisher's exact tests. As a sensitivity analysis, we will also analyze event rates using negative binomial models for each type of event, adjusting for each participant's length of follow-up.

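### Laboratory tests and vital signs are compared between arms only through a clinically significant yes/no flag; adding the measured values would cost little and, on stated assumptions, detect shifts about half to two-thirds as large

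*Combined protocol and SAP*

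**What the plan says.** Section 10.2.2.1 sets two binary endpoints. One is the proportion of subjects with "one or more TE clinically significant abnormal labs for each safety assay performed". The other is the same proportion for vital signs: "clinically significant abnormal vital signs for each vital sign monitored over 24 weeks in the inosine group will be compared to the placebo group". The test for both is Fisher's exact test. One-tailed testing at 0.05 is specified in the preceding sentence, on adverse events, and is not repeated for laboratory tests and vital signs. The sensitivity analysis, negative binomial models, also counts events.

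Section 9.1.1 says of the laboratory flag: "Clinically significant laboratory abnormalities, such as those that require intervention, are those that are identified as such by the Site Investigator". The same section lists "clinically significant abnormal test results (i.e. lab values or vital signs" among its examples of adverse events, without naming who judges vital signs. Neither has a numeric limit.

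The numbers themselves are collected. Under the Schedule of Activities and sections 8.1.1 and 8.1.2, blood pressure is taken at Screening, Week 12 and Week 20, and creatinine at Screening, Baseline, Week 12 and Week 20. Within section 10.2, measured laboratory values are summarised only as operational endpoints (serum urate and urine pH).

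**The concern.** Section 2.3.1 notes that "High urate levels have also been associated with high blood pressure and increased risk for cardiovascular events". Its reassurance from the earlier Parkinson's disease trial comes from measured values: "renal function measures of glomerular filtration rate and serum creatinine remained unchanged from baseline in all groups", with no effect on blood pressure either. The present trial has safety as a primary objective, yet it plans no estimate of the same kind.

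A yes/no flag keeps only whether a value crossed a line, and here the line is not written down. With ten placebo subjects, a flag that is rare on placebo gives the test little to work with. A moderate shift in mean blood pressure or creatinine could leave few subjects flagged, and the report would hold no between-arm estimate of it.

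**Working it through.** **Inputs from the documents.** Thirty treated subjects (section 5.1), randomised 2:1 (section 4.1), so 20 on inosine and 10 on placebo. Fisher's exact test (section 10.2.2.1). One-sided 0.05 is borrowed from the adverse-event sentence.

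**Assumptions.** The documents give no SD, no baseline correlation and no placebo flag rate for these measures. I assume a normal measure, a flag raised above a fixed cut-off, a pure mean shift under inosine, placebo flag rates p0 of 5, 10 and 20%, and baseline correlation r of 0, 0.5 or 0.7.

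**Step 1: reproduce the plan's own figures.** Section 10.2.2.5 gives 80% power for 95%, 71% and 59% on inosine against 50%, 20% and 10% on placebo. Exact one-sided Fisher power at 20:10, summed over both binomial distributions, is 79.7%, 80.1% and 79.7%. The figures reproduce, so the method matches the plan's.

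**Step 2: what the flag can detect.** With 0/10 flagged on placebo, the smallest significant result is 7/20 on inosine: C(20,7)/C(30,7) = 77,520/2,035,800 = 0.038. With 6/20 it is 38,760/593,775 = 0.065. For 80% power, find the inosine rate p1 by exact enumeration and convert it to a mean shift, z(p1) − z(p0):

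- p0 = 5%: p1 = 51.7%, shift 0.04 + 1.64 = 1.69 SD (unrounded)
- p0 = 10%: p1 = 59.1%, shift 0.23 + 1.28 = 1.51 SD
- p0 = 20%: p1 = 71.0%, shift 0.55 + 0.84 = 1.39 SD

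**Step 3: what the measured values can detect.** The standard error of a difference in means is sqrt(1/20 + 1/10) = 0.387 SD, multiplied by sqrt(1 − r²) after baseline adjustment. From the noncentral t distribution (28 df unadjusted, 27 adjusted), one-sided 0.05 and 80% power, the detectable difference is 0.99 SD at r = 0, 0.86 at r = 0.5 and 0.71 at r = 0.7.

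**Step 4: ratio of detectable shifts, measured value to flag.**

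| Placebo flag rate | Flag needs | r = 0 (0.99 SD) | r = 0.5 (0.86 SD) | r = 0.7 (0.71 SD) |
|---|---|---|---|---|
| 5% | 1.69 SD | 0.59 | 0.51 | 0.42 |
| 10% | 1.51 SD | 0.65 | 0.57 | 0.47 |
| 20% | 1.39 SD | 0.71 | 0.61 | 0.51 |

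A true shift of 0.99 SD, which the unadjusted measured values detect with 80% power, gives the flag 14%, 33% and 48% power at these three rates.

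**Step 5: sensitivity.**

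- *Two-sided 0.05 throughout:* the flag needs 1.76, 1.65 and 1.55 SD against 1.12 SD unadjusted, a ratio of 0.64 to 0.72.
- *15:15, as the Study Workflow shows:* 1.57, 1.46 and 1.36 SD against 0.93 SD, a ratio of 0.59 to 0.69. The conclusion does not depend on which allocation is right, though the two statements need reconciling.
- *Flag judged on change from the subject's own baseline:* its detectable shift is multiplied by sqrt(2(1 − r)). At r = 0.7 that is sqrt(0.6) = 0.775, giving 1.31, 1.17 and 1.08 SD. Against 0.71 SD the ratio is 0.54 to 0.65, so the gap narrows. At r = 0.5 the multiplier is 1 and nothing changes.

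**Step 6: what the added analysis would deliver.** The 95% interval half-width is 2.05 × 0.387 = 0.79 SD unadjusted, and 2.05 × 0.387 × sqrt(0.51) = 0.57 SD at r = 0.7.

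**The case against.** The best case for leaving the plan alone has several parts.

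- *Safety is defined through adverse events.* Section 3.2 says so, and the laboratory and vital-sign proportions are supportive. That stands, and it makes this an improvement rather than a defect in the primary analysis.
- *The kidney risk named in section 2.3.1 is stones.* These are already events of special interest with their own test. A reader might infer that the protocol names a gradual loss of renal function as a risk; it does not. Creatinine appears as a reassuring finding, and for blood pressure the protocol cites an association with urate but no effect of inosine in the earlier trials.
- *Potassium citrate might seem to require a between-arm potassium comparison.* Section 9.4 expects alkalinization at similar rates in both arms and section 9.4.2 monitors potassium closely, so that argument is weak.
- *The comparison in Step 4 favours the measured values.* Judgement may use the subject's own baseline, and the plan counts any abnormality over 24 weeks, not one reading. The first point is quantified in Step 5; the second is not modelled.
- *Local laboratories add noise to measured values too.* That is so. Baseline adjustment helps with a constant offset if a subject's samples stay at one laboratory.
- *The Medical Safety Monitor sees all safety laboratory tests quarterly* (section 10.1). A shift need not go unnoticed, but this is monitoring and yields no planned between-arm estimate.

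It is also tempting to read section 9.1.1 as giving the investigator the decision on vital signs. The text says so only for laboratory abnormalities: they "are those that are identified as such by the Site Investigator". For vital signs it is an inference.

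**Conclusion.** The gap is real and cheap to close. Laboratory tests and vital signs are compared only as an undefined flag and its event rate, while the numbers behind it are collected and left out of section 10.2. Under the Step 2 and 3 assumptions, measured values detect shifts 0.42 to 0.71 times the size the flag needs.

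A reader might shorten this to half the size. The documents do not support that without qualification: unadjusted, the ratio is 0.59 to 0.71, and a half needs baseline adjustment with a fairly strong correlation, or flags rarer than 5%. Nor would the added analysis let the trial declare no effect on blood pressure or renal function; the intervals are too wide for that. What it offers is an estimate with honest bounds where the plan now has none.

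**What to change.** In section 10.2.2.1:

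1. Keep the flag tables, and state sidedness and alpha for the laboratory and vital-sign comparisons.
2. Add baseline-adjusted between-arm differences, with confidence intervals, in measured systolic and diastolic blood pressure and serum creatinine/eGFR at Weeks 12 and 20. Use the shared-baseline model already specified for ALSFRS-R in section 10.2.2.3. Take the last pre-dose value as baseline; for vital signs that is Screening, since none are scheduled at the Baseline Visit.
3. Label these as exploratory estimates. Serum potassium may be summarised descriptively.

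The cost is a few lines of text and one short table, with no new visit, sample or clinical rule. The downside is a few more comparisons, and wide intervals that must not be reported as evidence of no effect.

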10.2.2.2 Tolerability

Tolerance will be defined as completion of the 20-week study without permanently discontinuing study drug or suspending study drug for greater than 28 days. Tolerability of inosine vs. placebo will be based on the proportion determined tolerant at week 20 and compared by Fisher's exact test from the AT sample. Serum urate elevation via oral inosine as titrated in this study will be judged tolerable if the lower one-sided 95% confidence bound on the proportion tolerant is greater than 50%.

10.2.2.3 Efficacy and target engagement

Effects of treatment on ALSFRS-R, will be analyzed in shared-baseline generalized least squares models with among-person effects of visit and the interaction of treatment group x post-baseline visit and within-person unstructured covariance among repeated measurements. Shared-baseline random-slopes linear mixed models will be used to analyze high-frequency smartphone metrics with fixed effects of time and treatment x post-baseline time and random participant-specific intercepts and slopes with unstructured covariance. Baseline characteristics will be compared by masked treatment groups prior to finalizing analysis of efficacy outcomes to select covariates to include the models to avoid chance confounding. Two-tailed tests at $\alpha = 0.05$ will be used.

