⁴ Screening labs include uric acid, urinalysis and Serum pregnancy test (WOCBP) and will be performed at local institution.

Inosine in ALS

V3.0

7/01/2019

⁵ Uric acid level will be measured just before the first dose (Baseline visit) or just before scheduled morning dose (trough) (Weeks 3, 6, 9, 12, 16, 20) (Quest Diagnostics)

⁶ Urinalysis with sediment (Quest Diagnostics)

⁷ Safety labs include Hematology (CBC with differential), Basic Metabolic Panel, Liver Function Tests and will be performed at local institution.

⁸ Pulmonary Function Testing includes Slow Vital Capacity (SVC)

⁹ Adverse events that occur AFTER signing consent form will be recorded.

¹⁰ App installation and un-installation procedures include a brief survey about phone use

STUDY WORKFLOW

[figure not shown]
Screening Period

On Active Treatment

Washout Period

[figure not shown]
[figure not shown]
~ 60 Screened

15 Subjects on inosine (administered as 500 mg caps; 1 to 6 caps a day; dose titrated to target urate levels of 7 - 8 mg/dL).

15 Subjects on placebo (administered as 500 mg caps; 1 to 6 caps a day; pseudo-titration will be performed to maintain blinding).

21 Days

Subjects who discontinue from the study early will be asked to return to the study site for Final Safety assessments, and will be asked to have a final Follow-Up Telephone Call 28 days (+5 days) after taking their last dose of study drug.

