Figure 2. Higher serum urate as a predictor of favorable clinical progression in early PD. Risk of progression is defined as *the hazard ratio of reaching disability sufficient to require dopaminergic therapy among 1,578 *de novo* PD subjects of the DATATOP and PRECEPT clinical trial cohorts. Values (mean and SD) are shown for increasing quintiles of serum urate measured at baseline, and are relative to the lowest quintile. Data are pooled (unpublished data, [name] *et al.*) from our prior publications on PRECEPT and DATATOP cohorts. The 1st, 3rd and 5th quintiles correspond to serum urate values of <4.1, 4.9-5.5 and >6.4 mg/dL, respectively.

[figure not shown]
Similar results were reported by other groups³²⁻³⁴ and were confirmed and expanded by our recent analysis of individuals from PRO-ACT, the largest available ALS clinical trial dataset (Pooled Resource Open-Access ALS Clinical Trials database)³⁵. In PRO-ACT, urate levels at trial entry were available for almost 1,800 individuals and were found to be one of the strongest predictors of disease progression and survival³⁵. Thus, higher levels of urate at trial entry were predictive of a slower drop in ALS functional rating scale-revised [ALSFRR-R (p=0.01)] and vital capacity [VC (p<0.0001)], and longer survival (p=0.02) in both men and women (³⁵ and [name] et al., unpublished data).

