5.2 Inclusion and Exclusion Criteria

5.2.1 Inclusion Criteria

Study subjects meeting all of the following criteria will be allowed to enroll in the study:

1. Age 18-85.
2. Sporadic or familial ALS diagnosed as possible, laboratory-supported probable, probable, or definite as defined by revised El Escorial criteria (Appendix 1).
3. Slow vital capacity (SVC) \geq 60% of predicted for age, height, and gender at the Screening Visit.
4. Capable of providing informed consent and following trial procedures.
5. Serum urate $<$ 5.5 mg/dL at screening (i.e. below the population median serum urate levels).
6. Women must not be able to become pregnant (e.g. post menopausal, surgically sterile, or using adequate birth control methods) for the duration of the study and 3 months after study completion. Adequate contraception includes: abstinence, hormonal contraception (oral contraception, implanted contraception, injected contraception or other hormonal (patch or contraceptive ring, for example) contraception), intrauterine device (IUD) in place for \geq 3 months, barrier method in conjunction with spermicide, or another adequate method.
7. Is able and willing to participate in the Mobile app study procedures.

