7.1 Screening Visit

The following procedures will be performed at an office visit to determine the subject's eligibility for the study:

- Obtain written informed consent from subject
- Assess inclusion and exclusion criteria
- Obtain medical history and demographics
- Obtain ALS diagnosis history
- Perform Pulmonary Function Tests (SVC)
- Perform physical examination
- Perform neurological examination
- Measure vital signs including height and weight
- Collect blood for screening labs
- Review and document concomitant medications and therapies
- Assess and document adverse events (AEs) that occur after subject signs informed consent form (ICF)

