10.2.2.5 Power Calculations

Assuming that 50%, 20%, and 10% of participants in the placebo group are expected to experience an AE or a given type of AE, we will have 80% power to declare a significant treatment-dependent increase in the proportion experiencing an AE if at least 95%, 71%, and 59% of participants in the inosine group are expected to experience an AE, respectively. We will have 80% power to observing at least one instance of any inosine-associated AE with a true probability of occurrence of at least 8%. For tolerability, we will have 80% power to declare inosine tolerable if the true proportion tolerant is at least 71%. Variance component estimates for calculating power for effects of treatment on ALSFRS-R are from a single arm pilot study of 25 participants on inosine for 20 weeks. Based on the follow-up schedule for this trial and assuming a random-slopes model, the estimated effective SD for ALSFRS-R slope per month is 1.4. Given this estimate, we will have 80% power to detect a difference in ALSFRS-R slopes between the inosine and placebo groups of 1.05 units per month. We will have 12% power for a difference in slopes of 0.3 units per month.

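### Efficacy covariates are chosen from observed baseline imbalance with no stated threshold, which costs some power against naming a prognostic covariate in advance; ITT rather than as-treated should be primary for efficacy

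*Combined protocol and SAP*

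**What the plan says.** Section 10.2.2.3 analyses ALSFRS-R with a shared-baseline generalized least squares model and the smartphone metrics with a shared-baseline random-slopes model. On covariates it says that "Baseline characteristics will be compared by masked treatment groups prior to finalizing analysis of efficacy outcomes to select covariates" for those models. The stated purpose is protection against chance confounding. No candidate list, measure of imbalance or cut-off is given. Efficacy tests are two-sided at 5%.

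Section 10.2.1 makes the as-treated (AT) sample primary for efficacy as well as for safety and tolerability. AT takes everyone dosed and groups them by what they actually received. ITT efficacy is secondary, with phase 3 planning as its purpose.

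Section 10.2.2.5 states that "the estimated effective SD for ALSFRS-R slope per month is 1.4", with 80% power for a difference of 1.05 units per month. Section 2.2.1 reports, from "our recent analysis of individuals from PRO-ACT, the largest available ALS clinical trial dataset", that "higher levels of urate at trial entry were predictive of a slower drop in ALS functional rating scale-revised" (p=0.01). Section 3.2 lists safety and tolerability as the primary outcomes; efficacy is not among them.

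**The concern.** A covariate improves precision because it predicts the outcome, not because the arms differ on it. A rule triggered by imbalance therefore leaves out a strong predictor in the trials where it is balanced and may bring in an irrelevant variable that is not. When the predictor is left out, its variance stays in the estimated standard error. The test is then conservative and power is lost. Masking does not change this, because the criterion itself is the problem.

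The AT choice is a separate matter. Grouping by treatment received can break the randomised comparison, which is the one a phase 3 plan needs.

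What is at stake is the precision and interpretation of a non-primary comparison in about 30 people.

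**Working it through.** **Inputs from the documents.** 30 treated (5.1); 2:1 allocation, so 20:10 (4.1), with 15:15 as a variant because the Study Workflow shows 15 per arm; difference 1.05 and SD 1.4 units per month (10.2.2.5); two-sided 5% (10.2.2.3).

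**Assumptions.** One continuous covariate with correlation ρ to the individual slope; 1.4 is the SD per participant; ANCOVA on slopes stands in for the planned models; selection is by p<0.05 to p<0.20, or by a standardized difference above 0.25, 0.20 or 0.10. The documents give none of these rules and no ρ.

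**The plan's own figure.** SE = 1.4 × √(1/20 + 1/10) = 0.542, and 1.05/0.542 = 1.94. With 28 degrees of freedom, exact t power is 46.4% (15:15: 50.9%). The stated 80% is not reproduced. That needs separate reconciliation, so a variant below takes 80% as given.

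**Fixed adjustment.** The residual SD is 1.4 × √(1−ρ²), which is 1.34 at ρ = 0.3 and 1.21 at ρ = 0.5, with 27 degrees of freedom. Integrating noncentral-t power over chance imbalance in the covariate gives the last column. The selection columns come from simulation with at least 100,000 trials per cell (Monte Carlo standard error at most √(0.25/100,000) = 0.16 points).

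| 20:10, power (%) | Never adjust | p<0.05 to p<0.20 | Std. difference >0.25 to >0.10 | Always adjust |
|---|---|---|---|---|
| ρ = 0.5 | 46.4 | 46.4-47.3 | 50.6-53.9 | 56.3 |
| ρ = 0.3 | 46.4 | 46.1-47.8 over all these rules | (same range) | 48.5 |
| ρ = 0.2 | 46.4 | no gain available | no gain available | 46.5 |
| ρ = 0 | 46.4 | – | – | 45.0 |

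Break-even is thus near ρ = 0.2, and an uninformative covariate costs 46.4 − 45.0 = 1.4 points.

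**15:15.** At ρ = 0.5, always adjusting gives 61.3%, against 51.2-52.3% (p-value rules) and 55.4-58.7% (standardized-difference rules).

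**Taking the plan's 80% as the unadjusted power (20:10).** At ρ = 0.5: 88.6% fixed, against 80.5-82.2% and 85.1-87.1%. At ρ = 0.3: 82.0% fixed, against 79.8-80.1% and 80.8-81.5%.

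**Type I error.** Under selection, null rejection is about 3.8-4.5% at ρ = 0.5 and about 4.5-4.9% at ρ = 0.3. With fixed adjustment it is about 5%.

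**Is urate strong enough?** Section 2.2.1 says "urate levels at trial entry were available for almost 1,800 individuals". If p=0.01 came from one linear test on all of them, t = 2.58 and r = 2.58/√(2.58² + 1,798) = 0.06. Entry requires urate below 5.5 mg/dL ("i.e. below the population median serum urate levels"). Cutting a normal distribution at its median leaves 1 − 2/π = 0.363 of the variance, so r falls to about 0.06 × √0.363 = 0.04. Both values are well below 0.2.

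**AT against ITT.** The samples differ only if someone randomised is never dosed or is regrouped. As an illustration, take one of 10 placebo participants whose slope lies 1.4 from a mean common to both arms and move that person to inosine. The estimated difference shifts by 1.4/9 + 1.4/21 = 0.22 units per month. The documents give no rate for such events, and section 7.2 has the first dose given on site at Baseline.

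**The case against.** The strongest reply is that the plan names no significance test for this step, so the loss depends on a rule the reader must supply. That stands. A reader might infer that selection forgoes most of the gain from adjustment. This holds for the p-value rules, but standardized-difference cuts of 0.25 to 0.10 keep 93-100% of the reduction in sampling variance and, at ρ = 0.5, a good part of the power. The documents support only that some power is lost, not that most of it is.

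The rule also has a legitimate aim, protection against chance imbalance in a small trial, decided on masked groups. A named prognostic covariate gives that protection for itself; for other covariates it moves to a sensitivity analysis, which is a real trade-off. Baseline ALSFRS-R is already handled by the shared-baseline models, so only other covariates are at issue.

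A reader might also infer that baseline urate is the natural covariate, being the predictor the protocol stresses. The protocol's own figures imply a correlation of about 0.04-0.06, at which adjusting slightly lowers power.

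On the analysis sample, ITT efficacy is already planned as secondary. Section 10.2.1 deals with inosine use in people who started on placebo by censoring them in a secondary safety analysis, which suggests AT leaves them in the placebo group. A material bias from AT is therefore not shown.

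**Conclusion.** The concern holds as a minor point. Selecting on imbalance is a weaker method than fixing a prognostic covariate in advance. At ρ = 0.3 or more, fixed adjustment beat every selection rule tried: by about 1 to 2 points at 0.3 and about 2 to 10 points at 0.5, under 20:10 and SD 1.4. At about 0.2 or below there is nothing to gain. The correlations and thresholds are assumptions, and ANCOVA on slopes only approximates the planned models.

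A reader might suspect an inflated false-positive rate; the calculation shows the opposite, a slightly conservative test. Making AT primary for efficacy is the wrong default in principle, with a small expected effect. No primary conclusion changes.

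**What to change.** In 10.2.2.3, replace the selection sentence with:

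> Before the masked groups are compared, one baseline covariate (at most two), chosen for known correlation with ALSFRS-R slope in external data, will be named in the SAP and included as a main effect and covariate x time regardless of balance; if none has a correlation above about 0.2, the models stay unadjusted. Covariates chosen for observed imbalance are used only in a sensitivity analysis.

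Screening SVC % predicted is a candidate already collected (7.1). Name baseline urate only if external data show a correlation above about 0.2 within the <5.5 mg/dL entry limit. PRO-ACT, which the team has already analysed, is the obvious source, if its records allow this trial's entry limits to be applied. The 25-participant pilot can serve only as a check: a correlation of 0.3 there has a 95% interval of −0.11 to 0.62.

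In 10.2.1, make ITT primary for efficacy with AT as sensitivity, and keep AT primary for safety and tolerability.

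The cost is SAP wording, one analysis of existing external data, and about 1.4 power points if the named covariate proves uninformative (about 3 for two). Chance imbalance in other covariates is then addressed only as sensitivity.
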